3.8 Sample Size

The primary objective of the proposed study is a composite of unplanned cardiovascular hospitalizations in AF patients and any AF-related emergency department visits. The sample size calculation is based on the test of the null hypothesis that the percentages of patients with cardiovascular hospitalizations in the two populations (CDSS and usual care) are equal. The primary measure of effect is the difference in proportions of patients with composite of any AF-related emergency department visit or unplanned CV hospitalization over 12 months. The criterion for significance (alpha) has been set at 0.05. With the proposed sample size of 1075 primary care patients (537 per intervention/control arm, assuming a 1:1 allocation ratio), the study will have power of 80% to yield a statistically significant absolute difference of 10% (or 20 [RRR] relative risk reduction) between the two percentages of patients with composite of any AF-related emergency department visit or unplanned CV hospitalization in the control and intervention groups, assuming 50% annual rate of CVD hospitalizations for the control group. This sample size was adjusted for a potential clustering of patient outcomes within a physician, by assuming an intra-physician correlation coefficient (ICC) of 0.05 with an average cluster size of 9 patients/physician. The ICC is based on studies done in the primary care sector reporting this magnitude of ICC. This extent of reduction was felt to represent a minimal clinically important achievement by a consensus of study investigators and has been an endpoint target in other studies in AF populations of similar design [127-129].

Table 3 provides a summary of the sample size calculation for different values of the baseline control rate (50%, 58%), RRR (15%, 20%, 25%, 30%), intra-class correlation coefficient [ICC] (0.05, 0.10) and average cluster size (m) (9,12,15). The primary measure of effect is the difference in the proportions or percentages of patients with cardiovascular hospitalizations and AF-related emergency room visits across study arms over an active study period of 12 months. The criterion for significance (alpha) has been set at 0.05. The test is 2-tailed, which means that an effect in either direction will be interpreted. The statistical power is set at 80%.

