The analysis and reporting of the trial results will follow the CONSORT Statement for cluster-randomization trials [129]. The baseline characteristics of the practices and patients will be reported by group as mean (standard deviation) or median (first quartile, third quartile) for continuous variables, depending on the distribution, and count (percent) for categorical variables. The analysis will follow the intention-to-treat (ITT) principle. The unit of randomization will be the practice. The unit of analysis will be the patient. We will use multiple imputation to handle missing data to enable ITT analysis. Multiple imputation is a Monte Carlo technique in which the missing values are replaced by $m > 1$ simulated versions, where 'm' is typically small. Each of the simulated complete datasets will be analyzed by standard methods, and the results will be combined to produce estimates and confidence intervals that incorporate missing data uncertainty [133]. We will use generalized estimating equations (GEE) – assuming exchangeable correlation structure for patients within the same practice, and adjusting for urban and rural practice types to analyse all outcomes [130]. Unlike ordinary regression techniques, GEE allows us to model the intra-practice correlation among patients within each practice. The results will be reported as the estimate of the effect, corresponding 95% confidence interval and associated p-values. All p-values will be reported to three decimal places with those less than 0.001 reported as $p < 0.001$. The criterion for statistical significance will be set a priori at $\alpha = 0.05$, and adjusted using the Bonferroni method for multiple secondary analyses. All analyses will be performed using SAS 9.4 (Cary, NC).

Sensitivity analyses: 1) There are several methods for analyzing cluster RCTs [131]. Therefore, we will perform sensitivity analyses using some of the commonly used patient-level methods such as random-intercept model and cluster-level (i.e. random- and fixed-effects meta-analytic) methods to assess the robustness of the results. 2) Given that the unit of randomization is the practice, there is a higher chance of potential imbalance of patient-level baseline characteristics. We will perform some sensitivity analysis to adjust for any potential imbalance.

HRQoL

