The proportion of patients with reported impairment in each of the five EQ-5D-5L dimensions will be calculated for each arm. Health utilities will be calculated using the Canadian EQ-5D-5L scoring algorithm. QALYs accumulated over the study period will be calculated using the area under the curve method.

Costs

Total cost will be calculated using the sum of the product of resource utilization items (e.g. length of hospital stay, medications) and corresponding unit costs.

Cost effectiveness

The incremental cost effectiveness ratio (ICER) will be calculated by dividing the incremental difference in the mean cost between the treatment arms by the incremental difference in the mean QALYs between the arms. Sampling uncertainty is a critical issue that needs to be sufficiently and adequately dealt with in any economic evaluation alongside a clinical trial.

CONFIDENTIAL

Nonparametric bootstrap with replacement will be used to estimate the confidence intervals around the ICER. The decision uncertainty will be presented using the cost effectiveness acceptability curves in which maximum willingness to pay value from the policy maker's perspective is explicitly considered. Both base case and uncertainty analyses will be stratified by demographic and socioeconomic variables (such as age, gender and income). These stratified analyses are important for any economic evaluation to identify subpopulations that could potentially receive the most benefit from the intervention.

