will be conducted by calculating the incremental cost per QALY gained by the CDSS arm compared with the usual care arm. Due to skewness of costs and health utility distributions, the non-parametric bootstrapping method will be used to estimate the 95% confidence interval for the incremental cost per QALY gained. All analyses will be performed using SAS version 9.4 (Cary, NC).

Secondary Outcomes Analysis

We will estimate the effect of CDSS (intervention) versus usual care (control) over 12 months on the following: any AF-related emergency department visit; unplanned CV hospitalization; strokes; systemic embolism / major bleeding; mortality; anticoagulant therapy; access to specialist consultation; echo; catheter ablations; EQ5D; health care costs (Table 3). The subgroup analyses will be performed by adding an interaction term of the subgroup variable and the intervention variable in the model. The criterion for statistical significance for subgroup analyses will be set at alpha = 0.05. This will not be adjusted for multiple testing as these analyses are exploratory.

Sensitivity Analyses

There are several methods for analyzing cluster RCTs^{17, 18}. We will conduct sensitivity analyses in two ways. Firstly, we will perform sensitivity analyses using commonly used patient-level methods such as random-intercept model method (Table 4a). Secondly, we will also perform sensitivity analyses with the outcome (composite of any AF-related emergency department visit or unplanned CV hospitalization) being treated as a count assuming a Poisson distribution (Table 2). The results will be reported as incidence rate ratio [IRR], 95% CI and associated p-value. We hypothesize that our results will remain robust to the different sensitivity analyses.

Subgroup Analyses

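### Neither document says that the ICER bootstrap resamples practices; read naturally it resamples patients, which gives too narrow an interval if costs or QALYs cluster within practice

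*Protocol*

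**What the plan says.** On the design, Protocol section 3.9 states "The unit of randomization will be the practice" and "The unit of analysis will be the patient"; the SAP (Primary Outcome Analysis) takes the same position. Protocol section 3.7.1 stratifies the randomization by urban or rural location.

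On clustering in general, section 3.9 uses GEE, "assuming exchangeable correlation structure for patients within the same practice, and adjusting for urban and rural practice types to analyse all outcomes". The SAP repeats this, and its Table 1 lists EQ5D and health care costs among the outcomes to be analysed by GEE or frailty models.

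On cost-effectiveness, section 3.9 obtains the ICER by "dividing the incremental difference in the mean cost between the treatment arms by the incremental difference in the mean QALYs between the arms". It then says "Nonparametric bootstrap with replacement will be used to estimate the confidence intervals around the ICER" and adds acceptability curves. The SAP says "the non-parametric bootstrapping method will be used to estimate the 95% confidence interval for the incremental cost per QALY gained", and introduces the method with "Due to skewness of costs and health utility distributions".

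Neither document names the resampling unit. Neither mentions a cluster or two-stage bootstrap, or a multilevel cost-effectiveness model.

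**The concern.** A bootstrap interval reflects the sampling variation that the resampling imitates. If patients are drawn one by one, those of the same practice are treated as independent, and the between-practice part of the variance of an arm mean is largely lost. The plan takes clustering seriously elsewhere: it raises the sample size by 40% for it and models it with GEE. The ICER is not estimated from the GEE, though. It is a ratio of differences in unadjusted arm means with a separate interval method, chosen for skewness, and skewness and clustering are different problems.

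The ICER interval and the acceptability curves are what a policy maker would use, and section 3.1 says the trial is designed for that reader. If practices are left out of the resampling, both convey more certainty than the design supports. Section 3.9 itself insists that sampling uncertainty be handled adequately in an economic evaluation.

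**Working it through.** **Inputs from the documents**
- ICC 0.05 and average cluster size m = 9, for the primary clinical outcome (Protocol section 3.8). The same section also considers ICC 0.10 and, in Table 3, m = 12 and 15.
- VIF = 1 + (m − 1) × ICC (section 3.8).
- At least 15 enrolled patients per provider (section 4.1).
- 200 providers (sections 3.1 and 3.7.2).

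**Assumed, because the documents give no figure**
- An ICC shared by costs and QALYs: 0, 0.01, 0.05 or 0.10.

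**The plan's own figure.** With control rate 0.50, intervention rate 0.40 and rounded z values:
- Total n = 2 × (1.96 + 0.84)² × (0.50×0.50 + 0.40×0.60) / 0.10² = 2 × 7.84 × 0.49 / 0.01 = 768.32.
- VIF = 1 + 8 × 0.05 = 1.4, and 768.32 × 1.4 = 1075.65, the stated 1075. The formula and inputs are therefore read as the plan intends.

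**Coverage of an interval that treats patients as independent.** An ICER interval rests on a linear combination of cost and QALY differences. If that combination has variance inflation VIF, the patient-level interval is 1/√VIF of the correct width, and its coverage is 2Φ(1.96/√VIF) − 1.

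| m | ICC | VIF | Width relative to correct | Coverage of nominal 95% |
|---|---|---|---|---|
| 9 | 0 | 1.00 | 1.00 | 95.0% |
| 9 | 0.01 | 1.08 | 0.96 | 94.1% |
| 9 | 0.05 | 1.40 | 0.85 | 90.2% |
| 9 | 0.10 | 1.80 | 0.75 | 85.6% |
| 15 | 0.05 | 1.70 | 0.77 | 86.7% |
| 15 | 0.10 | 2.40 | 0.65 | 79.4% |

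If each of the 200 providers were its own cluster, m = 1075/200 = 5.4. At ICC 0.05 the VIF is 1.22 and coverage 92.4%.

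**Simulation of the ICER interval itself**, because the formula is for a normal mean rather than a ratio. Assumptions: skewed costs with SD 6000, QALY SD 0.2, true differences of 400 and 0.05, independent practice effects on cost and QALY, and equal cluster sizes. The number of practices follows from the sample size: 1075/9 is about 60 per arm, and 1075/15 about 36. Percentile intervals were used, with 1,000 runs of 300 resamples (1,500 of 500 at ICC 0). The Monte Carlo standard error is about 0.5 to 1.1 points.

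| Practices per arm | m | ICC | Coverage, resampling patients | Coverage, resampling practices |
|---|---|---|---|---|
| 60 | 9 | 0 | 95.3% | 94.3% |
| 60 | 9 | 0.01 | 94.9% | 94.5% |
| 60 | 9 | 0.05 | 91.7% | 95.4% |
| 60 | 9 | 0.10 | 87.6% | 96.2% |
| 36 | 15 | 0.05 | 86.3% | 94.4% |

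For net benefit, on which acceptability curves rest, at an assumed 50,000 per QALY and ICC 0.05, coverage was 90.9% against 95.4% (m = 9) and 85.7% against 92.2% (m = 15). Resampling practices was slightly short in the last case, with 36 practices per arm, but still much closer to 95%.

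**The case against.** The strongest objection is that the text does not say what it is faulted for. Resampling whole practices is also a nonparametric bootstrap with replacement, so a competent analyst could do the right thing without departing from either document. A reader might infer that the plan prescribes patient-level resampling and that its interval is therefore shown to be wrong. The documents do not support that: they are silent on the unit. What remains is that the declared unit of analysis, the raw arm means and the skewness rationale all point to patients, and nothing points to practices.

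Second, the plan applies GEE to all outcomes, and SAP Table 1 names EQ5D and costs. This stands for those separate comparisons, so it would be wrong to say that the economic data get no clustering adjustment. It does not reach the ICER interval or the acceptability curves, which have their own estimator and method. The SAP's cluster-related sensitivity analyses concern the clinical outcomes only.

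Third, a reader might infer that cost-effectiveness belongs to the primary research question. Protocol section 2.1 asks about health care costs and resource use, not about an ICER or QALYs, and section 2.2 places the ICER among the secondary outcomes.

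Fourth, the ICC of 0.05 is borrowed from a binary clinical outcome. That is fair, and it is why a range is shown; at 0.01 the effect is close to negligible.

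**Conclusion.** The gap is real and should be closed, but it is one of specification in a secondary analysis. Followed in its natural reading, the plan gives an ICER interval and acceptability curves that ignore randomization by practice. The direction of the error is clear whenever the cost–QALY combination is positively correlated within practice. Its size is not known from the documents. With 9 patients per practice, coverage of a nominal 95% interval runs from about 94% (ICC 0.01) through 90% (0.05) to 86% (0.10); with 15 patients and 0.05 it is about 87%.

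These figures assume one ICC for costs and QALYs and equal cluster sizes. The cluster size is itself uncertain: section 3.8 gives 9 per physician, whereas practices are randomized and may hold several providers, which would raise m, while one provider per cluster would lower it to about 5.4. The primary outcome analysis is not affected.

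**What to change.** State in Protocol section 3.9 and in the SAP's economic paragraph that the bootstrap draws whole practices with replacement, separately within arm and urban/rural stratum; that each patient's cost and QALY stay paired; and that the same replicates supply the ICER interval and the acceptability curves. A two-stage bootstrap or a bivariate multilevel model for cost and QALY would also serve, if named in advance.

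The same text should say how the bootstrap is combined with the multiple imputation in section 3.9, and that the analyses stratified by age, gender and income also resample practices.

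No new data or patients are needed. The cost is a short addition to the text, a little extra code (mainly for the imputation step), and wider intervals where clustering is present: √1.4 = 1.18 times as wide at ICC 0.05 and m = 9 by the formula, and about 1.24 times in median width for the simulated ICER.

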A subgroup analysis will be conducted to compare the effect of CDSS (intervention) versus usual care (control) on the composite of any AF-related emergency department visit or unplanned CV hospitalization, as well as the of number AF Related ED Visits and CV Hospitalizations individually, by location of practice, patient sex, age, CHADS2, CHADS-VASC, hypertension, diabetes and years of practice of family doctor. We will perform these subgroup analyses by regression methods with appropriate interaction terms. This subgroup analysis will be conducted for all primary and secondary outcomes (Tables 5a, 5b and 5c). Our hypothesis is that the effects of the intervention on outcomes differ by subgroups. A sensitivity analysis will equally be conducted for all the different subgroup analyses with the outcome being treated as a count (Tables 5a, 5b and 5c). All the subgroup results will be presented using forest plots reporting estimates of effect as HR or IRR, 95% CI for each subgroup and a p-value of the interaction test.

Dissemination

Upon trial completion, the primary manuscript with the 12-month follow-up results, whether positive, negative or neutral, will be submitted for a peer-reviewed publication to a top medical journal. The final dataset will be shared through an open access data repository once all analyses are completed.

References

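### The stratified cost-effectiveness analysis is meant to find who benefits most, but neither document specifies a test of whether strata differ in cost-effectiveness, and income has no interaction test at all

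*Protocol*

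**What the plan says.** The cost-effectiveness paragraph of Protocol section 3.9 defines the ICER as the difference in mean cost over the difference in mean QALYs. "Nonparametric bootstrap with replacement will be used to estimate the confidence intervals around the ICER", and acceptability curves are to show decision uncertainty. It then adds: "Both base case and uncertainty analyses will be stratified by demographic and socioeconomic variables (such as age, gender and income"), in order "to identify subpopulations that could potentially receive the most benefit from the intervention". No cut-points, number of levels, contrast between strata or exploratory label is given for this step.

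The SAP (cost-effectiveness text under Primary Outcome Analysis) says "the non-parametric bootstrapping method will be used to estimate the 95% confidence interval for the incremental cost per QALY gained". It mentions no stratification of that analysis.

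For subgroups in general, the SAP does set a method: "The subgroup analyses will be performed by adding an interaction term of the subgroup variable and the intervention variable in the model". The factors are "by location of practice, patient sex, age, CHADS2, CHADS-VASC, hypertension, diabetes and years of practice of family doctor". The Subgroup Analyses section and Table 1 extend this to every primary and secondary outcome, and that list includes EQ5D and health care costs. The ICER and net benefit are not listed outcomes, and income is not a listed factor. Tables 5a to 5c have shells only for the composite, AF-related ED visits and CV hospitalizations. The SAP calls its subgroup analyses exploratory and leaves them unadjusted for multiplicity.

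**The concern.** Finding out who benefits most is a comparison between strata. A bootstrap interval or an acceptability curve within each stratum describes uncertainty inside that stratum and says nothing direct about the difference between two of them. The ICER is also a poor scale for the comparison. A negative ratio can mean fewer QALYs at higher cost or more QALYs at lower cost, so stratum ICERs have no consistent order once either difference changes sign.

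The protocol presents the trial as serving policy makers (section 3.1) and cites interest in how interventions work according to ability to pay (section 1.3). A report that the CDSS looks cost-effective in one income or age group and dominated in another (dearer and with fewer QALYs) would therefore attract attention. It could arise from noise around one common effect.

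**Working it through.** **The plan's own figure.** The only sample size is for the primary composite: 50% against 40%, two-sided alpha 0.05, 80% power, ICC 0.05, 9 patients per cluster. Total n = 2 × (1.96 + 0.84)² × (0.25 + 0.24) / 0.10² = 768.32. Multiplied by 1 + 8 × 0.05 = 1.4, this is 1075.6, which matches the stated 1075. Nothing is calculated for the economic strata.

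**Inputs.** From Protocol section 3.8: 537 per arm, ICC 0.05, cluster size 9, represented here as 60 practices of 9 per arm (540). Assumed, because the documents give no value: QALY SD 0.20 (range 0.15 to 0.25); the same true gain of 0.01 in every patient (range 0.005 to 0.02); ICC 0.05 also for QALYs and costs; three half-splits of the same patients, standing in for age, sex and income; cost and QALY uncorrelated.

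**One split, QALY sign.**
- A patient has on average 8/2 = 4 practice companions in the same stratum, so the design effect within a stratum is 1 + 4 × 0.05 = 1.2.
- Variance of a stratum's QALY difference = 2 × 0.20² × 1.2 / 270 = 0.000356; SE = 0.0189.
- The two strata share practices. Covariance = 2 × 60 × (9 × 8 / 4) × 0.05 × 0.20² / 270² = 0.0000593; correlation = 0.0000593 / 0.000356 = 0.17.
- P(a given stratum is negative) = Φ(−0.01 / 0.0189) = 0.298. P(both negative), from the bivariate normal with correlation 0.17, is 0.109.
- P(opposite signs) = 2 × (0.298 − 0.109) = 0.38.

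**Three splits of the same patients.** These share one overall estimate, so the joint probability was simulated. At least one split shows opposite QALY signs in about 60% of trials. Over the SD and gain ranges above, the figure is about 25 to 68%.

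**One stratum dominated and its counterpart not, in at least one of three splits** (same QALY assumptions; true cost effect in units of the SE of the overall cost difference):
- costlier by 1 SE: about 55%
- cost-neutral: about 41 to 43% across simulation runs
- cost-saving by 1 SE: about 23%
- cost-saving by 2 SE: about 8%

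**A second layout.** Take two age, two sex and three income levels, with cost-QALY correlation 0 or −0.3 and effects in units of the overall SE. The chance that at least one of the seven strata has a dominated point estimate is:
- no true effect on cost or QALYs: 69 to 74%
- cost-neutral with a QALY gain of 1 to 2 SE: 18 to 51%
- QALY gain and cost saving both 2.8 SE: 0.5 to 2%

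These figures include trials in which the whole-trial estimate is dominated too. Excluding those, the first becomes 42 to 43% and the last stays at 0.5 to 2%.

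**For comparison.** With one interaction test at 0.05 for each of three factors, treated as independent, the chance of any false signal is 1 − 0.95³ = 14.3%.

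**The case against.** Four points on the other side carry weight.

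First, a reader might infer that the economic outcomes have no interaction tests at all. The SAP text does not support that. It requires interaction terms for all secondary outcomes, EQ5D and costs are among them, and age and sex are among the factors. What stands is narrower. Testing costs and EQ5D one at a time does not test cost-effectiveness, which depends on both jointly. Income is tested on no outcome, and the table shells show neither economic outcome.

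Second, the protocol does not propose to rank bare ICERs. The uncertainty analyses are stratified too, acceptability curves remain readable when a difference changes sign, and the aim is hedged to groups that might benefit. No roll-out rule is stated. This softens the point but still supplies no contrast between strata.

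Third, a reader might infer that chance will often make one stratum look dominated. That is conditional on the true economic effect. The trial expects fewer admissions and lower costs, and if both gains and savings are clear the risk is small. It is also tempting to treat the strata and splits as independent, giving 2 × 0.298 × 0.702 = 0.42 for one split and 1 − 0.58³ = 0.80 for three. That overstates the matter, because the splits divide the same patients and the strata share practices. Nor is a negative QALY difference alone dominance, which needs higher cost as well.

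Fourth, the SAP, dated 2019, describes only the overall cost per QALY, so the stratified analysis may no longer be intended. The SAP does not say that it was dropped, and the protocol still contains it.

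**Conclusion.** The point holds in a limited form. The protocol plans stratified cost-effectiveness results to locate the groups that benefit most. Neither document specifies a between-stratum contrast on the ICER or net benefit, income has no interaction test anywhere, and the SAP does not carry the stratification forward.

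The risk of a misleading pattern is material if the true economic effect is null or modest: about 60% for opposite QALY signs in at least one of three splits, and about 41 to 55% for discordant dominance when costs are neutral or higher by 1 SE. It falls to a few per cent or less if gains and savings are both clear. All of these figures rest on the assumed SD, gain, ICC, strata and cost-QALY correlation. None of those values for the economic outcomes comes from the documents. This is a worthwhile improvement to a secondary analysis. It does not affect the primary comparison or patient safety.

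**What to change.** In the cost-effectiveness paragraph of Protocol section 3.9 and the matching SAP text:

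- Base subgroup comparisons on individual net monetary benefit, NMB = λ × QALY − cost, where λ is each willingness-to-pay value already needed for the acceptability curves.
- Regress NMB on arm, subgroup and arm-by-subgroup, with practice-clustered standard errors and adjustment for urban or rural practice.
- Report incremental net benefit in each subgroup, with the interaction estimate, 95% CI and p-value.
- Add income to the factors, state the cut-points in advance, label the analysis exploratory, and make no subgroup claim from separate stratum ICERs alone.
- If the stratified analysis is no longer intended, say so in the SAP.

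The cost is wording in two documents and one regression per factor and willingness-to-pay value. Household income, EQ-5D-5L and resource use are already to be collected.

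There are two downsides. Results depend on λ, so they must be shown at several values. The interaction test also has low power. On the QALY scale, under the same assumptions, the SE of the difference between two half-strata is 0.0189 × √(2 × (1 − 0.17)) = 0.024. The SE of the overall effect is 0.20 × √(2 × 1.4 / 540) = 0.0144, so the former is about 1.7 times as large. A non-significant interaction would therefore not show that the strata are alike.
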